### 9.2 Statistical Hypotheses

For primary endpoint: we hypothesize that the proportion of patients who died in the HBOT group will be lower than that in the SOC group. We will test the hypothesis against the null of no difference in proportions of incident mortality.

For secondary end points:

1. We hypothesize that the proportion of patient who need mechanical ventilation in the HBOT group will be lower than that in the SOC group. We will test the hypothesis against the null of no difference in proportions between the two groups.
2. We further hypothesize that the patients in the HBOT group will spend on average fewer number of days on a ventilator compared to those in the SOC group. We will test the hypothesis against the null that there is no difference in means between the two groups.

Safety analysis: We hypothesize that the rate of any severe adverse effects will be smaller in the HBOT group compared to the SOC group. We will test the hypothesis against the null of no difference.

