#### **4.2.2 Secondary Study Endpoints**

The secondary endpoints will be whether a patient needed invasive mechanical ventilation and the number of days on a ventilator for those who did receive ventilation. The rate of patients who needed mechanical ventilation among those who received hyperbaric oxygen will be compared to the rate in a matched cohort of patients that received standard of care and did not get hyperbaric oxygen.

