### 9.4 Description of Statistical Methods

#### 9.4.1 General Approach

We will summarize the continuous variables using mean, median, standard deviation and ranges, and the categorical variables using frequency and proportions. Variables will also be summarized graphically. Baseline characteristics of the participants who received HBOT will be compared with that of control patients receiving SOC. If we find any significant difference in the baseline variables between the two matched groups, we will adjust for them as covariates in outcome analysis. T-test or ANOVA will be used for continuous variables whereas chi-squared test will be used for comparison of proportions. All tests will be two tailed at significance level of 0.05. Appropriate transformations (such as log transformation) will be considered for any continuous variable that indicates non-normality. Statistical software R and SAS will be used for the analysis.

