#### **9.4.3 Analysis of the Secondary Endpoint(s)**

The first secondary endpoint is a binary outcome indicating whether a patient needed a mechanical ventilation. We will compute the proportion of patients who needed mechanical ventilation during their treatment for each matched group. The proportion in HBOT arm will be compared with that in matched SOC using chi-square test for proportions. Estimate of difference in proportion along with 95% confidence interval will be reported. Similar to the primary analysis, we will adjust for any potential confounders, deemed important in the baseline analysis, by using multivariable logistic regression. Estimate of odds-ratio and 95% confidence interval will be reported.

To compare the average number of days spent in ventilator between the two groups, we will use linear regression analysis. The distribution of outcome, the number of days in ventilator, will be assessed graphically and by conducting test for normality. If we find the evidence of deviation from normal distribution the outcome will be log transformed before proceeding with analysis. We will also adjust for any potential confounders, deemed important in the baseline analysis. Slope coefficient along with 95% confidence interval will be reported as an estimate of difference between HBOT and SOC groups.

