### **9.5 Sample Size**

Using a sample of 160 patients, 40 in HBOT arm and 120 in SOC arm (post matching) we can detect a reduction of 22.5% or higher, against the null of no difference, with 80% power at significance level of 0.05, assuming that the mortality rate in SOC arm is about 80%.

For the secondary analysis, our proposed sample of 160 patients will similarly allow us to detect a difference of 22.5% in need for ventilation between HBOT group and SOC group with 80% power. For comparing the continuous outcome of number of days in ventilation, we have 80% power to detect effect size (cohen's d) of 0.51 with 160 patients.

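### Ventilator days are scored so that fewer is better, with no rule for death and no settled population, so the result cannot by itself be read as benefit or harm

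*Combined protocol and SAP*

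**What the plan says.** Section 4.2.2 defines the second secondary endpoint as "the number of days on a ventilator for those who did receive ventilation". Section 9.2 sets the favourable direction, "We further hypothesize that the patients in the HBOT group will spend on average fewer number of days on a ventilator", and adds: "We will test the hypothesis against the null that there is no difference in means between the two groups". Section 9.4.3 gives the method: "To compare the average number of days spent in ventilator between the two groups, we will use linear regression analysis". It adjusts for baseline confounders only, and "If we find the evidence of deviation from normal distribution the outcome will be log transformed before proceeding with analysis". Section 9.4.1 fixes the error rate: "All tests will be two tailed at significance level of 0.05".

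On power, Section 9.5 says of this endpoint: "we have 80% power to detect effect size (cohen's d) of 0.51 with 160 patients". The same section sizes the primary comparison "assuming that the mortality rate in SOC arm is about 80" per cent, and Section 9.4.2 gives about 80% as the SOC need for mechanical ventilation.

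No section says how a death on the ventilator is counted. There is no worst score for death, ventilator-free-days definition, competing-risk method or survivor-only analysis. There is no fixed time horizon either, because participation lasts for the hospital stay (Section 5.6). Mortality is analysed separately as the primary endpoint and is not linked to ventilator days.

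**The concern.** Time on a ventilator ends at death as well as at extubation. A patient who dies on ventilator day 2 contributes 2 days. One who is extubated alive on day 14 contributes 14 and counts as the worse result.

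The population adds a second difficulty. Intubated patients are excluded at entry (Section 5.2), so ventilation is a later event, and the first secondary hypothesis is that HBOT reduces it. Comparing only those who were ventilated conditions on an outcome that treatment may change, and baseline matching does not protect that comparison. Sections 9.2, 9.4.3 and 9.5, however, refer to the groups or to 160 patients without this restriction.

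At stake is whether a significant result here means anything. Fewer days could reflect faster recovery, earlier death or a different mix of ventilated patients. Section 9.1 defers the formal SAP to the end of an unblinded study, so a rule for death would otherwise be chosen with the data in view.

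**Working it through.** **1. The plan's own figure.** Inputs: 40 HBOT, 120 SOC, two-sided 0.05, 80% power (Sections 9.4.1 and 9.5). Detectable d = (1.960 + 0.842) × √(1/40 + 1/120) = 2.802 × 0.1826 = 0.511. The stated 0.51 reproduces, but only with all 160 patients counted.

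Restricted to ventilated patients as in Section 4.2.2:
- 80% ventilated in both groups (32 v 96): d = 0.572, and power at d = 0.51 is 0.705.
- HBOT ventilation down to 57.5% (23 v 96): d = 0.650, and power at d = 0.51 is 0.594.

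So Sections 4.2.2 and 9.5 describe different populations.

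**2. How common death is among the ventilated.** SOC mortality 0.80 (Section 9.5) and SOC ventilation 0.80 (Section 9.4.2):
- P(ventilated and dead) ≥ 0.80 + 0.80 − 1 = 0.60.
- P(dead given ventilated) ≥ 0.60 / 0.80 = 0.75.

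On the plan's figures, most SOC ventilator counts end in death.

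**3. Effect on the mean, ventilated patients only.** Let c be fatality among the ventilated, D the days to death and S the days to live extubation. Mean days = c × D + (1 − c) × S. If D and S are the same in both groups, HBOT minus SOC = (c_SOC − c_HBOT) × (S − D).

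Assumptions: c = 0.80 v 0.575. This is the plan's mortality with its 22.5% reduction read as percentage points (that reading gives power 0.787, against 0.62 if relative), applied to ventilated patients. D and S are not in the documents, so a range is shown. Ventilator-free days (VFD) to an assumed day 28, with death = 0, are (1 − c) × (28 − S).

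| D / S | SOC mean days | HBOT mean days | Difference | VFD, SOC v HBOT |
|---|---|---|---|---|
| 7 / 14 | 8.40 | 9.98 | +1.58 | 2.80 v 5.95 |
| 7 / 21 | 9.80 | 12.95 | +3.15 | 1.40 v 2.98 |
| 10 / 10 | 10.00 | 10.00 | 0 | 3.60 v 7.65 |
| 14 / 10 | 13.20 | 12.30 | −0.90 | 3.60 v 7.65 |

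HBOT saves the same 22.5 points of mortality in every row and has no effect on duration within survivors or within those who die. The ventilator-day difference nevertheless changes sign with the assumed timing of death.

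**4. All 160 patients, never-ventilated scored 0.** Mean = v × [c × D + (1 − c) × S], where v is the proportion ventilated.
- v = 0.80 in both groups: the differences in step 3 shrink by a factor of 0.80 (7/14: +1.26; 14/10: −0.72).
- v falling from 0.80 to 0.575, 7/14: 0.80 × 8.40 = 6.72 v 0.575 × 9.975 = 5.74, difference −0.98. With the same fall in ventilation but no survival benefit, HBOT would be 0.575 × 8.40 = 4.83, difference −1.89. Saving lives here reduces the apparent gain.

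A patient who dies without being ventilated scores 0, the best possible value, and log(0) is undefined for the planned transformation.

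**5. How often the test would mislead.** Simulation with 32 v 96 ventilated patients, gamma times (shape 2, assumed), a t-test on log days and 3,000 runs.
- Mortality benefit (80% to 57.5%): significant against HBOT in 14.6% of runs for 7/14 and 28.5% for 7/21, and in its favour in at most 0.2%. For 14/10 it is 0.6% against and 7.4% in favour.
- Mortality harm (57.5% to 80%): significant in favour of HBOT in 14.3% for 7/14 and 24.2% for 7/21.
- VFD with death = 0, compared by Mann-Whitney in the same ventilated patients: favours HBOT in 62% (7/14) and 52% (7/21) of benefit runs, and in none of the harm runs.

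**The case against.** The strongest reply is that this is the second secondary endpoint of a non-randomised pilot. Mortality is primary, need for ventilation comes first among the secondaries, and both are reported with confidence intervals, so a reader will see deaths beside ventilator days. That stands and limits the severity: in the simulated benefit cases the usual result is non-significant, not reversed.

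Days on a ventilator also have meaning as resource use, since the rationale cites pressure on ventilators. That supports keeping the figure as description. It does not support testing it as a benefit in which fewer is better.

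A reader might infer that the endpoint penalises HBOT for saving lives. The documents do not support that as a general statement. It requires those who die to leave the ventilator sooner than survivors, and no durations are given. At equal times the bias is zero, and if deaths come later it runs towards HBOT.

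A reader might also take the restriction to ventilated patients as settled. Only Section 4.2.2 states it, and Section 9.5 counts all 160. On the all-patient reading, with ventilation falling to 57.5%, the 7/14 example favours HBOT and the subset argument falls away. The missing rule for death does not.

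Finally, the 75% bound combines two 80% figures that appear in near-identical sentences in Sections 9.4.2 and 9.5, one labelled ventilation and the other mortality. If one label is a slip, the bound weakens. The scoring defect does not depend on it.

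**Conclusion.** The point holds and should be fixed. The plan treats fewer ventilator days as better, has no rule for death, and defines the endpoint in one population while powering it in another. On its own rates, at least 75% of ventilated SOC patients die, so this is not a marginal case. With a 22.5-point mortality difference among the ventilated and no true effect on duration, the spurious difference in means runs from −0.90 to +3.15 days over the durations tried. Those durations, the application of the planned mortality rates to ventilated patients, the gamma shape and the 28-day horizon are assumptions.

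The conclusion is that the result cannot by itself be read as benefit or harm, in either direction. It would go too far to say that the endpoint will make HBOT look worse, or that the trial's main conclusion is compromised: the primary mortality comparison is unaffected.

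**What to change.** In Sections 4.2.2, 9.2 and 9.4.3, and in the Endpoint row of the Protocol Summary, replace the tested endpoint with ventilator-free days to day 28 in all 160 patients, and change the hypothesis to more ventilator-free days with HBOT.
- **Scoring:** any death by day 28 scores 0 (worst), and never-ventilated survivors score 28. Patients discharged alive are taken as alive and ventilator-free.
- **Start of count:** the first HBOT session. For SOC, use a defined index day, such as the day the patient first met the eligibility criteria.
- **Analysis:** at 80% SOC mortality about 96 of 120 SOC scores would be 0 if those deaths fall by day 28, so linear or log regression is unsuitable. Use a Wilcoxon rank-sum test, or proportional-odds regression when adjusting for covariates.
- **Power:** remove or restate the d = 0.51 statement in Section 9.5.
- **Description:** keep ventilator days among ventilated patients as an untested measure of ventilator use, shown separately for survivors and non-survivors.

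The cost is modest but goes beyond wording. The SOC index day must be defined and extracted. Dates of death and discharge are already among the data to be collected (Section 13), and ventilator dates are needed for the present endpoint. The downside is that the score mixes death with duration and assumes status after discharge.

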Objectives	Determine Safety and Efficacy of Hyperbaric Oxygen as an adjunctive treatment for COVID 19 hospitalized patients
Methodology	This is a prospective interventional cohort study that will evaluate the risks and benefits of HBOT utilization for COVID-19 confirmed patients in the hospital setting.
Endpoint	Primary endpoint: Death Secondary endpoints: Need for invasive mechanical ventilation, reduction in days on a ventilator Safety endpoints: Incidence of adverse events (AE) and severe adverse events (SAE)
Study Duration	Approximately two months, but subject to change given the nature of the ongoing pandemic.
Participant Duration	Duration of inpatient hospitalization.
Intervention	Up to 5 hyperbaric oxygen treatments at 2.0 ATA for 90 minutes dependent on the ability of the patient to participate
Population	Patients greater than 18 years of age diagnosed with COVID19 and under respiratory distress.

CONFIDENTIAL

This material is the property of the NYU School of Medicine and Langone Medical Center. Do not disclose or use except as authorized in writing by the study sponsor

Eligibility Criteria	
Inclusion criteria:
 
 
1. Laboratory confirmed COVID-19 positive or a clear clinical diagnosis of COVID-19
 
2. SpO2 <93% after trial of non-rebreather with no less than 85% SpO2
 
3. At least 18 years of age
 
4. No absolute contraindication for Hyperbaric Oxygen
 
 
Exclusion criteria:
 
 
1. Pregnancy
 
2. Untreated Pneumothorax
 

Study Sites	
NYU Winthrop Hospital          NYU Langone School of Medicine          Northwell Hospital          Cleveland Clinic          Loma Linda          Jacobi/Einstein          University of Kentucky Hospital          Westchester Medical Center          Geisinger Commonwealth School of Medicine          Spectrum Health Hospital          University of Illinois at Urbana-Champaign

Number of participants	
40 patients in severe respiratory distress          (SpO2 < 93% on RA, but oxygen responsive)

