### **2.4 Potential Risks & Benefits**

#### **2.4.1 Known Potential Risks**

##### Risks Associated with Hyperbaric Therapy:

The risks of hyperbaric oxygen are well reported. Hyperbaric oxygenation typically requires constant care and may be difficult for individuals experiencing nausea or vomiting, claustrophobia, or altered mental status from lack of oxygen. The most common side effects that you may feel, because of the high pressure and small space, include fatigue, lightheadedness, anxiety or claustrophobia, and ear discomfort which can be a pain and a “popping” feeling. More severe side effects include fluid buildup of the middle ear, sinus damage, trauma from the increased air pressure (baurotrauma), change in vision, oxygen toxicity seizures, and development of collapsed lungs (pneumothorax). Development of a pneumothorax may result in cardiopulmonary collapse, and ultimately death. However, patients will be instructed on how to prevent these side effects and the oxygen dose given to participants will be determined specifically by healthcare providers who will take into consideration participants' overall health and age to reduce complications.

There also exists the risk of recurrence of symptoms after exiting from the chamber. Furthermore, there exists the risk of cross contamination/exposure of other strains of COVID-19, however all the chambers will be set up specifically for COVID-19 positive patients and will be thoroughly cleaned after used in order to reduce risk of cross-contamination. Due to the oxygen rich environment there is an increased inherent fire risk. Due to the novelty of COVID-19, the risks of hyperbaric oxygen specifically for COVID-19 patients are currently unknown.

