## **5.7 Total Number of Participants and Sites**

There are a total number of 11 sites. All sites will submit their own individual IRB proposal to be approved by their respective institution's IRB. NYU is the lead site and the Co-Principal Investigators, [name] and [name], will be the lead coordinators of this study.

Recruitment will end when approximately 40 participants are enrolled in the HBOT group.

We will create a comparison cohort from chart review of 120 patients who received standard treatment and were matched with 40 HBOT patients in 3:1 ratio, such that the comparison group will consist of 120 standard of care patients. For this retrospective comparison group, we will be requesting a waiver of consent and authorization for this cohort.

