#### **9.4.4 Safety Analyses**

To assess severe adverse events (SAEs), we will consider otic barotrauma, myopia, oxygen toxicity seizures and acute pulmonary edema. For each patient we will count the total number of SAEs during hospitalization.

SAEs will be summarized by computing mean and standard deviation for each comparison group. We will further compare mean number of SAEs between HBOT and SOC groups using linear regression. The outcome will be log transformed to account for the potential violation of normality. We will report difference in mean along with 95% confidence interval around the mean.

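### Safety is framed as a superiority test on mean event counts; it should be estimated as HBOT-arm incidence with exact confidence limits

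*Combined protocol and SAP*

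**What the plan says.** Section 9.2 sets the safety hypothesis: "We hypothesize that the rate of any severe adverse effects will be smaller in the HBOT group compared to the SOC group". The next sentence gives the test: "We will test the hypothesis against the null of no difference". Section 9.4.1 adds: "All tests will be two tailed at significance level of 0.05".

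Section 9.4.4 names four events (ear barotrauma, oxygen toxicity seizures, acute pulmonary edema and myopia), counts them per patient over the hospital stay, and summarises the counts by mean and standard deviation. It then says: "We will further compare mean number of SAEs between HBOT and SOC groups using linear regression". The count is log transformed, and a difference in means with a 95% interval is reported.

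The Protocol Summary defines the endpoint differently: "Safety endpoints: Incidence of adverse events (AE) and severe adverse events (SAE". Sections 4.2.3 and 8.1 list the same four events as potentially related to HBOT. On the state of knowledge, section 2.4.1 says that "the risks of hyperbaric oxygen specifically for COVID-19 patients are currently unknown".

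The sample size in section 9.5 covers mortality, need for ventilation and ventilator days. The documents give no power, expected event rate, margin or largest acceptable risk for safety.

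**The concern.** Safety is one of the trial's two stated purposes (section 3), and the risks in this population are described as unknown. The natural safety question is how often patients given HBOT have harmful events, and how large a risk the data still allow. Section 9.2 asks something else, namely whether HBOT patients have fewer severe events than controls. For barotrauma, oxygen toxicity seizures and vision change, which section 2.4.1 itself lists as side effects of HBOT, a reduction relative to patients who were never pressurised is hard to motivate.

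The planned summary does not fill the gap. A mean count, or a difference in means on a log scale, does not give the proportion of HBOT patients affected or an upper limit for it. With 40 treated patients, a non-significant comparison is compatible with a wide range of harm, and the plan has no rule for reading such a result. Section 9.1 defers the formal SAP to the end of a non-blinded study, so the reading should be fixed beforehand.

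**Working it through.** **Inputs.** Group sizes are from section 9.5 ("Using a sample of 160 patients, 40 in HBOT arm and 120 in SOC arm (post matching") and section 5.7 ("matched with 40 HBOT patients in 3:1 ratio"). The two-sided 0.05 level is from section 9.4.1. Event rates are assumptions, because the documents give none.

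**The plan's own figure.** There is none for safety. As a check on the group sizes, take the efficacy claim in section 9.5: 80% power for 80% v 57.5% (80% minus 22.5 points). The pooled rate is (0.575×40 + 0.80×120)/160 = 0.744. The null SE is √[0.744×0.256×(1/40 + 1/120)] = 0.0797, and the alternative SE is √(0.575×0.425/40 + 0.80×0.20/120) = 0.0863. Power is Φ[(0.225 − 1.96×0.0797)/0.0863] = Φ(0.797) = 79%, which agrees with the stated 80%.

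**Step 1: chance of missing a true HBOT excess.** As a proxy for the planned regression, compare the proportions of patients with at least one event using the uncorrected Pearson test. Enumerate all 41 × 121 outcomes with probability Bin(a; 40, p_H) × Bin(b; 120, p_S), and sum those significant with HBOT worse. The miss rate is 1 minus that sum.

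| HBOT v SOC (assumed) | Excess, points | Missed |
|---|---|---|
| 10% v 0% | 10 | 8% |
| 10% v 1% | 9 | 26% |
| 5% v 0% | 5 | 40% |
| 10% v 2% | 8 | 41% |
| 20% v 10% | 10 | 60% |
| 5% v 1% | 4 | 66% |
| 6% v 2% | 4 | 73% |
| 10% v 5% | 5 | 77% |
| 15% v 10% | 5 | 84% |

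The first row can be checked by hand. With no SOC events, one HBOT event gives chi-squared 3.02 and two give 6.08, against a critical value of 3.84, so at least two are needed. The miss rate is 0.90^40 + 40×0.10×0.90^39 = 0.0148 + 0.0657 = 0.080. The result at an SOC rate of zero is sensitive to the test: Fisher's exact test would miss 22% (10% v 0%) and 68% (5% v 0%).

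**Step 2: does the proxy mislead?** The planned regression was simulated with Poisson counts and log(count + 1), 20,000 runs. Both the Poisson model and the +1 are assumptions. Mean counts of 0.10 v 0.05 (HBOT v SOC) were missed 78% of the time, and 0.20 v 0.10 were missed 65%. These are close to the proxy's 77% and 60%.

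**Step 3: what the stated hypothesis needs.** Even with 0/40 HBOT events, significance for a reduction requires at least 11/120 SOC patients (9.2%) with an event: chi-squared is 3.94 for 11 and 3.56 for 10. If the analysed events are rarer than that in SOC, the hypothesis can hardly be confirmed.

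**Step 4: what the HBOT arm alone can exclude.** With zero events in n patients, the two-sided exact 95% upper limit is 1 − 0.025^(1/n).

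- n = 40: 8.8% (one-sided 95%, 1 − 0.05^(1/40): 7.2%).
- n = 10, at the pause: 30.8% (one-sided: 25.9%).

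**Step 5: what the difference can exclude.** With a common rate p, the 95% half-width is 1.96×√[p(1 − p)(1/40 + 1/120)]. This is 7.8 points at p = 5% and 10.7 points at p = 10%.

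**The case against.** The strongest reply is that the test is not blind to harm. It is two-tailed, a 95% interval is planned, and the directional sentence in section 9.2 expresses an expectation without altering the test. That stands. A large harm, or a sizeable excess of events nearly absent in SOC, would often be detected.

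Second, a reduction is not always an odd alternative. Under the definition of serious events in section 8.3, SAEs include death and life-threatening deterioration, which HBOT is hoped to reduce. Section 2.3 describes pulmonary edema as part of the disease, section 2.5 credits HBOT with reducing edema, and section 2.4.1 does not list pulmonary edema as an HBOT risk. That also stands. The mismatch is clearest for the pressure- and oxygen-related events.

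Third, safety does not rest on this test alone. All AEs are collected, individual data are listed, there are reviews at 10, 20 and 40 patients, and section 9.4.1 promises frequencies and proportions for categorical variables. This narrows the gap without closing it. Section 9.4.4 does not apply proportions to safety, and no within-arm confidence limit is planned.

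A reader might infer that the plan would declare HBOT safe on a non-significant result, or that harm would probably be missed whatever its form. The documents support neither. No section equates non-significance with safety, and the miss rate can be as low as 8% when SOC patients have no events, which is the setting to expect for events specific to HBOT.

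A non-inferiority margin is an alternative remedy. At 40 v 120 with equal true rates, the smallest margin giving 80% power (one-sided 0.025) is about 11 points at a 5% event rate and 15 points at 10%, so estimation suits this pilot better.

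**Conclusion.** The point holds as a mismatch between the safety question and the planned analysis. The hypothesis is superiority, the endpoint is incidence, and the planned output is a difference in log-transformed mean counts that cannot say what HBOT risk has been ruled out. A non-significant result would carry little information. Under the assumed rates, an excess of 4 to 10 points is missed between 8% and 84% of the time, and the SOC rate largely decides where in that range. The zero-event limits, 8.8% for 40 patients and 30.8% for 10, need no assumed rate. The miss rates rest on the assumed rates, on a binary proxy for the count regression and on an unpaired calculation that ignores the matching. The weakness is one of framing and reporting; it does not mean that the analysis could never reveal harm.

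**What to change.** - **Section 9.2:** replace the superiority safety hypothesis with an estimation aim, namely to estimate the incidence of adverse events in patients given HBOT.
- **Section 9.4.4:** make the main safety result the number and percentage of HBOT patients with at least one AE, at least one SAE, and each HBOT-related event, each with an exact (Clopper-Pearson) 95% interval.
- **Between-group comparison:** report the HBOT minus SOC difference in proportions with its 95% interval as supportive.
- **Interpretation:** state in advance that p > 0.05 is not evidence of safety and that the conclusion will be based on the upper confidence limit.

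The cost is protocol and SAP wording plus a few exact intervals, with no new data and no change to treatment. The drawback for the sponsor is a less favourable safety statement: even an event-free HBOT arm could be reported only as a risk not shown to be below 8.8%.
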